6.2.2. Analysis Methods for Secondary Efficacy Endpoints

Number of subjects with $\geq 30\%$ or $\geq 50\%$ PSA reduction from baseline at 12 weeks and during the whole treatment period will be summarized separately.

The number and percentage of subjects in each overall response category by lesion scans (eg, CR, PR, SD, and PD) will be summarized by treatment group for the FAS.

The analysis of OS will be performed using the Kaplan-Meier method for the FAS Analysis Set. Medians, Q1, Q3, the proportion of subjects who have no events at 24 weeks and 48 weeks from the first dosing date will be provided along with corresponding 95% CIs. Kaplan-Meier curves for OS will be provided by treatment group.

7. SAFETY ANALYSES

7.1. Adverse Events and Deaths

7.1.1. Adverse Event Dictionary

Clinical and laboratory adverse events (AEs) will be coded using the current version of MedDRA. System organ class (SOC), high-level group term (HLGT), high-level term (HLT), preferred term (PT), and lower-level term (LLT) will be provided in the AE dataset.

7.1.2. Adverse Event Severity

Adverse events are graded by the investigator as Grade 1, 2, 3, 4, or 5 according to CTCAE Version 4.03. The severity grade of events for which the investigator did not record severity will be categorized as “missing” for tabular summaries and data listings. The missing category will be listed last in summary presentation.

7.1.3. Relationship of Adverse Events to Study Drug

Related AEs are those for which the investigator selected “Related” on the AE case report form (CRF) to the question of “Related to Study Treatment.” Relatedness will always default to the investigator’s choice, not that of the medical monitor. Events for which the investigator did not record relationship to study drug will be considered related to study drug for summary purposes. However, by-subject data listings will show the relationship as missing.

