### **5.3. Dosage and Administration of GS-5829 and Enzalutamide**

GS-5829 tablets will be provided by Gilead Sciences, Inc. and will be taken orally. Initiation of treatment with the study drug will take place after enrollment and cohort assignment. Subjects will take their dose of study drug at approximately 24-hour intervals. To reduce inter-subject variability on efficacy and safety, subjects will be instructed to take GS-5829 approximately 1 hour before or 2 hours after a meal, unless otherwise specified by protocol. Grapefruit juice is prohibited while on study drug. In one or more monotherapy dose levels or in the monotherapy expansion (Group 1), on Day 1 of Cycle 2, approximately 10 subjects may be asked to administer GS-5829 in fed state with a standardized meal (~500 to 600 calories and ~30% of calories from fat). If evaluation of food effect cannot be performed on Cycle 2, Day 1, it may be performed at a visit after Cycle 2, Day 1 (where subject has taken at least 7 consecutive days of GS-5829), if necessary.

XTANDI® (enzalutamide) will be supplied as 40 mg capsules for oral administration. Subjects assigned to receive enzalutamide in combination with GS-5829 in this study will orally self-administer 4 capsules of enzalutamide (160 mg total daily dose) once daily at approximately 24-hour intervals beginning on Study Day 1 and GS-5829 will start, at the assigned dose, 14 days ( $\pm$  3 day window) later on Cycle 1 Day 1. Subjects enrolled into Group 3 should be on at least 12 weeks of continuous enzalutamide treatment prior to starting Cycle 1 Day 1. Capsules should be swallowed whole and may be taken with or without food. Refer to [Appendix 9](#) for further details.

If the subject misses a dose, he should be instructed to take the study drug as soon as he remembers, unless more than 8 hours have elapsed since the scheduled time of the missed dose. In this case, the subject should be instructed to wait and take the next dose at the regularly scheduled time. Subjects should not take more than 1 dose of study drug at a time.

If a subject vomits within 5 minutes of dosing and the tablet is visible, the subject should be instructed to re-dose. If a subject vomits more than 5 minutes after dosing or if the tablet is not visible, the subject should be instructed to wait and take the next dose at the regularly scheduled time.

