**Table 5-2. Dose Reduction in Group 2: Combination of Enzalutamide and GS-5829**

	Considered related to enzalutamide	Considered related to GS-5829	Considered potentially related to both enzalutamide and GS-5829 or unknown relationship
Grade 4 toxicity	Interrupt dosing of enzalutamide for at least 7 days and not longer than 17 days until symptoms improve to $\leq$ Grade 2, then resume at 120 mg. If subject is already at 120 mg, or it takes longer than 17 days to improve $\leq$ Grade 2, then permanently discontinue both enzalutamide and GS-5829.	Permanently discontinue both enzalutamide and GS-5829	Permanently discontinue both enzalutamide and GS-5829
Grade 3 toxicity	Interrupt dosing of enzalutamide for at least 7 days and a maximum of 17 days until symptoms improve to $\leq$ Grade 2, then resume at 120 mg. If subject is already at 120 mg, or it takes longer than 17 days to improve $\leq$ Grade 2, then permanently discontinue both enzalutamide and GS-5829.	Interrupt GS-5289 for a maximum of 28 days until the toxicity resolves to $\leq$ Grade 1 or returns to baseline level. Following resolution of the toxicity or the toxicity returns to baseline level, treatment may be restarted at a reduced dose as per Table 5-1 .  Enzalutamide dosing does not need to be interrupted or dose reduced.	Interrupt both enzalutamide and GS-5829 for at least 7 days and a maximum of 17 days until symptoms improve to $\leq$ Grade 1 or return to baseline level at which time subjects may resume enzalutamide at either 120 mg or 160 mg and resume GS-5829 at a reduced dose per Table 5-1 . If a subject is already at 120 mg of enzalutamide, they must discontinue.

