1.2. Study Design

This study has two phases: Phase 1b dose escalation and Phase 2 dose expansion.

Phase 1b: This is an open-label, multicenter, sequential dose-escalation study to evaluate the safety, tolerability, PK, and pharmacodynamics (PD) of GS-5829 as a single agent, and combined with enzalutamide in subjects with metastatic castrate-resistant prostate cancer (mCRPC).

Dose Escalation of GS-5829

Subjects with mCRPC who have progressed on either abiraterone and/or enzalutamide will be sequentially enrolled at progressively higher dose levels to receive oral GS-5829 as a single agent once daily. Dose escalation [3+3] will be performed with cohort sizes of 3 to 6 subjects. Initially 3-4 subjects will be enrolled into each dose level. The study will be initiated at a dose level that has been demonstrated to be safe and tolerable in the ongoing Phase 1 study in patients with solid tumors and lymphomas (Study GS-US-350-1599).

The dose levels for single agent GS-5829 once daily are 2, 3, 4, 6 and 9mg. Dose levels may be modified based on emerging safety, PK, PD, and efficacy results.

Dose Escalation of GS-5829 and enzalutamide

The combination dose escalation using 3+3 design may initiate prior to identification of the MTD of single agent GS-5829 using a starting dose of GS-5829 that has been determined to be safe and tolerable in the single agent dose escalation. The first 3-4 subjects to enroll will receive GS-5829 at a dose less than or equal to the previously determined single agent MTD (or a monotherapy dose that has been determined to be safe) combined with enzalutamide.

Enzalutamide is a strong CYP3A4 inducer, which is expected to decrease the exposure of GS-5829 and therefore a higher dose of GS-5829 may be required to achieve target coverage compared to the single agent dose. Subjects will administer enzalutamide 160 mg once daily as a single agent starting on Study Day 1 through Cycle 1, Day 1. On Cycle 1 Day 1 (approximately 14 days after Study Day 1), subjects will administer GS-5829 once daily in combination with enzalutamide 160 mg once daily in order to evaluate the interaction of the 2 agents. Depending on the observed PK interaction, toxicity and tolerability observed in the single agent dose escalation, the dose escalation may continue beyond a dose which has been identified to be safe and tolerable in the single agent arm. Any increase in the dose of GS-5829 will not be by more than 100% in the next cohort.

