3.1.2. Full Analysis Set

The Full Analysis Set (FAS) includes all subjects who took at least 1 dose of study drug with treatment group designated according to the planned treatment. This is the primary analysis set for efficacy analyses. Throughout this SAP, study drug is defined as any drug in the therapy (GS-5829 or enzalutamide) unless specified otherwise.

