7.1.5. Treatment-Emergent Adverse Events

7.1.5.1. Definition of Treatment-Emergent Adverse Events

Treatment-emergent adverse events (TEAEs) are defined as 1 or both of the following:

- Any AEs with an onset date on or after the study drug start date and no later than 30 days after permanent discontinuation of study drug
- Any AEs leading to premature discontinuation of study drug.

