7.1.6.1. Summaries of AE Incidence by Severity Grades

The number and percentage of subjects who experienced at least 1 TEAE will be provided and summarized by SOC, HLT PT, and treatment group. For other AEs described below, summaries will be provided by SOC, PT, and treatment group:

- TEAEs
- TEAEs with Grade 3 or higher
- TEAEs related to GS-5829
- TE SAEs

- TE SAEs related to GS-5829
- TEAEs leading to premature discontinuation of GS-5829
- TEAEs leading to death
- TEAEs leading to temporary interruption of GS-5829
- TEAEs leading to dose reduction of GS-5829

A brief, high-level summary of AEs described above will be provided by treatment group and by the number and percentage of subjects who experienced the above AEs.

Multiple events will be counted only once per subject in each summary. Adverse events will be summarized and listed first in alphabetic order of SOC and HLT within each SOC (if applicable), and then by PT in descending order of total frequency within each SOC. For summaries by severity grade, the most severe grade will be used for those AEs that occurred more than once in an individual subject during the study.

In addition to the above summary tables, all TEAEs and TE SAEs will be summarized by PT only, in descending order of total frequency. All TEAEs and TEAEs related to GS-5829 will be summarized by SOC, PT and severity.

In addition, data listings will be provided for the following:

- All AEs, indicating whether the event is treatment emergent
- All AEs with Grade 3 or higher
- All SAEs
- All deaths
- All AEs leading to death
- AEs leading to premature discontinuation of GS-5829
- AEs leading to temporary interruption of GS-5829
- AEs leading to dose reduction of GS-5829

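### In the combination cohorts, the SAP's GS-5829-related adverse event summaries can count events from the enzalutamide-only run-in and events attributed only to enzalutamide

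*SAP*

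**What the plan says.** Four provisions of the SAP act together.

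- **Study drug.** SAP 3.1.2: "Throughout this SAP, study drug is defined as any drug in the therapy (GS-5829 or enzalutamide) unless specified otherwise".
- **Treatment emergence.** SAP 7.1.5.1 includes "Any AEs with an onset date on or after the study drug start date", up to 30 days after permanent discontinuation.
- **Relatedness.** SAP 7.1.3 begins "Related AEs are those for which the investigator selected" the related option on one CRF question, which asks about study treatment and not about a named drug. For unanswered items: "Events for which the investigator did not record relationship to study drug will be considered related to study drug for summary purposes". Listings keep such values as missing.
- **Summaries.** SAP 7.1.6.1 lists "TEAEs related to GS-5829" and the matching table of serious events. The first is also broken down by system organ class, preferred term and severity.

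The dosing sequence is in SAP 1.2: "Subjects will administer enzalutamide 160 mg once daily as a single agent starting on Study Day 1 through Cycle 1, Day 1". Protocol 5.3 gives the interval: "GS-5829 will start, at the assigned dose, 14 days" later, with a window of 3 days either way.

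Protocol 8.6.2 also has one related/unrelated category, not split by drug, and plans a summary of study-drug-related events. The GS-5829 label on the table therefore first appears in the SAP, while SAP 7.8 declares no change from the protocol's safety analyses.

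**The concern.** The tables claim causality for GS-5829, but the rule behind them establishes causality only for the regimen. In a combination subject the regimen starts with two weeks of another drug.

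Safety and tolerability of GS-5829, alone and with enzalutamide, is a primary phase 1b objective, and SAP section 1 records that only phase 1b was run. DLTs are reported as a listing (SAP 7.1.7.1), so these two summaries are the only planned aggregate tables of events by causality to GS-5829.

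The toxicity profiles overlap. Protocol 1.5 names fatigue and dizziness among the known effects of enzalutamide, and also among the events considered related to GS-5829 in the first-in-human study. For such events, timing and investigator attribution are what separate the drugs, and the stated rule uses neither. A reader who compares the combination columns with the monotherapy columns could then see an excess of GS-5829-related events that comes from enzalutamide.

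**Working it through.** The plan states no figure on this point, so the check is a trace of the definitions, followed by simple arithmetic on the run-in.

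**Step 1: three cases taken through the SAP as written**

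| Case | Treatment-emergent? (SAP 3.1.2, 7.1.5.1) | Related? (SAP 7.1.3) | In the GS-5829-related summary? (SAP 7.1.6.1) |
|---|---|---|---|
| Event on run-in day 5, attributed to enzalutamide | Yes, study drug began on Study Day 1 | Yes, related to study treatment | Yes, although no GS-5829 has been taken |
| Same event, item left blank | Yes | Yes, by default | Yes, same result |
| Event after Cycle 1 Day 1, attributed only to enzalutamide | Yes | Yes | Yes |

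No other provision derives relatedness to GS-5829 or sets an onset limit at the first GS-5829 dose. Cases 1 and 3 do not need the missing-value default. It adds only case 2, so the main cause is the non-specific item combined with the broad definition of study drug.

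**Step 2: where the documents do separate the drugs**

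- SAP 3.1.4 counts the DLT period in days of GS-5829.
- SAP 4.1 gives discontinuation reasons for each drug, and SAP 4.2.1 measures GS-5829 exposure.
- Protocol 3.2 requires a DLT to be possibly related to GS-5829.
- Protocol Table 5-2 has a column for enzalutamide, a column for GS-5829, and a third headed "Considered potentially related to both enzalutamide and GS-5829 or unknown relationship".

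**Step 3: size of the run-in**

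Inputs: run-in r = 14 days, range 11 to 17 (Protocol 5.3); 28 days of GS-5829 to the end of the DLT period. The share of time without GS-5829 is r/(r + 28):

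- r = 11: 11/39 = 28%
- r = 14: 14/42 = 33%
- r = 17: 17/45 = 38%

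TEAEs are collected for longer than this, so the share falls as treatment continues. Two assumed durations with r = 14 show the range. With 8 weeks of GS-5829 plus 30 days of follow-up it is 14/(14 + 56 + 30) = 14%. Over 24 weeks of GS-5829 it is 14/(14 + 168) = 8%. These are shares of time at risk, not of events.

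**Step 4: effect of one subject**

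One reclassified subject in a cohort of n moves incidence by 1/n: 33 points for n = 3, 25 for n = 4, 17 for n = 6. Subjects count once per summary, so overall incidence moves only if that subject has no other event already counted as related.

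**Step 5: are run-in events recorded?**

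Protocol 6.4.1, read literally, restricts AE form entries to serious and procedure-related events until the Cycle 1 Day 1 dose. The opening of Protocol section 6 and Protocol 7.3.1 and 7.3.2 move to full recording at the first investigational product or study medication, which in these cohorts is enzalutamide. The sections conflict for non-serious run-in events. Serious events are recorded under either reading, so the serious-event table is open to the problem in any case.

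**The case against.** The strongest reply is that misattribution is possible but not shown. The SAP is based on an eCRF that is not in the documents. Table 5-2 requires attribution by drug, and the SAP already handles discontinuation by drug. The eCRF may therefore hold a relatedness item for each drug, with SAP 7.1.3 written as template shorthand. That is plausible, and it limits the claim to what the text permits. It does not remove the gap. If per-drug items exist, SAP 7.1.3 does not name the one used or map blanks to a drug. If only the combined item exists, the table titles claim more than the data hold.

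Second, setting a blank to related is a conservative default, and the listings preserve the missing value. This stands: the default is a secondary cause, and it needs only an onset limit.

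Third, a reader might infer that the phase 1b safety objective for the combination is answered with misattributed events. The documents do not support that. The phase 1b primary endpoint is DLT incidence. DLTs require possible relation to GS-5829, and their window is counted in GS-5829 days, so DLT and MTD determination excludes the run-in. All TEAEs, Grade 3 or higher TEAEs, serious TEAEs and deaths are also summarized without regard to cause. Monotherapy cohorts have no run-in.

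Fourth, a subject who leaves during the run-in stays in the Safety Analysis Set and could dilute a GS-5829 rate (1/3 would become 1/4). No document reports such a subject, and SAP 3.1.4 deliberately keeps replaced subjects in that set. Changing the denominator is a matter of choice.

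**Conclusion.** The concern holds in a limited form. Followed as written, the SAP can place run-in events and enzalutamide-only events in the combination columns of the GS-5829-related TEAE summary, its severity breakdown, and the GS-5829-related serious TEAE summary. Nothing else in the safety analysis is shown to be affected.

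The documents give no adverse event rates, no rate of unanswered relatedness items and no eCRF, so the number of misattributed events cannot be estimated. The 33% share of early time (28% to 38% over the window) and the 17 to 33 points per subject show how sensitive small cohorts are. They do not estimate bias. The conclusion assumes that SAP 7.1.3 is applied literally. Its reach for non-serious run-in events also depends on how the conflict over recording is settled.

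**What to change.** For the combination cohorts, in SAP 7.1.3 and 7.1.6.1:

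1. Name the eCRF item that defines relatedness to GS-5829. Count an event as GS-5829-related only if its onset is on or after the first GS-5829 dose and the investigator attributed it to GS-5829 or to both drugs.
2. Apply the missing-means-related default to GS-5829 only for onsets on or after that dose.
3. Show run-in events separately, from Study Day 1 to before the first GS-5829 dose.
4. If the eCRF holds only the combined item, retitle the tables as related to study treatment.
5. Record the change in SAP 7.8, or in the clinical study report if the SAP is already final.

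Protocol 6.4.1 must be reconciled with the opening of section 6 and with 7.3.1 and 7.3.2 on what is recorded during the run-in, and the SAP should state which data the run-in summary contains. A denominator of subjects with at least one GS-5829 dose is optional.

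The cost is SAP wording, some programming and one more column in the combination tables. No new data are needed: the onset limit uses dose dates already required for the exposure analysis and the enzalutamide administration listing.

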7.1.4. Serious Adverse Events

Serious adverse events (SAEs) will be identified and captured as SAEs if the AEs met the definitions of SAE that were specified in the study protocol. SAEs captured and stored in the clinical database will be reconciled with the SAE database from the Gilead Pharmacovigilance and Epidemiology Department before data finalization.

7.1.5. Treatment-Emergent Adverse Events

7.1.5.1. Definition of Treatment-Emergent Adverse Events

Treatment-emergent adverse events (TEAEs) are defined as 1 or both of the following:

- Any AEs with an onset date on or after the study drug start date and no later than 30 days after permanent discontinuation of study drug
- Any AEs leading to premature discontinuation of study drug.

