### **7.2.2. Assessment of Severity**

The severity of AEs will be graded using the CTCAE, Version 4.03 ([Appendix 6](#)).

For each episode, the highest severity grade attained should be reported.

If a CTCAE criterion does not exist, the investigator should use the grade or adjectives: Grade 1 (mild), Grade 2 (moderate), Grade 3 (severe), Grade 4 (life-threatening), or Grade 5 (fatal) to describe the maximum intensity of the AE. For purposes of consistency with the CTCAE, these intensity grades are defined in [Table 7-1](#).

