## **8.6.2. Adverse Events**

All AEs will be listed. The focus of AE summarization will be on treatment-emergent AEs. A treatment-emergent AE is defined as an AE that occurs or worsens in the period from the first dose of study drug to 30 days after the last dose of study drug.

AEs will be coded using the Medical Dictionary for Regulatory Activities (MedDRA <http://www.meddramsso.com>) with descriptions by System Organ Class (SOC), High-Level Group Term, High-Level Term, Preferred Term, and Lower-Level Term. The severity of AEs will be graded by the investigator according to the CTCAE, Version 4.03, whenever possible. If a CTCAE criterion does not exist for a specific type of AE, the grade corresponding to the appropriate adjective will be used by the investigator to describe the maximum intensity of the AE: Grade 1 (mild), Grade 2 (moderate), Grade 3 (severe), Grade 4 (life threatening), or Grade 5 (fatal). The relationship of the AE to the IP will be categorized as related or unrelated.

TEAEs will be summarized by dose level. Summary tables will be presented to show the number of subjects reporting treatment-emergent AEs by severity grade and corresponding percentages. A subject who reports multiple treatment-emergent AEs within the same Preferred Term (or SOC) is counted only once for that Preferred Term (or SOC) using the worst severity grade. AE descriptions will be presented by decreasing frequency for a given SOC and Preferred Term. Separate listings and summaries will be prepared for the following types of treatment emergent AEs:

- Study-drug-related AEs
- AEs that are Grade  $\geq 3$  in severity
- AEs leading to study drug interruption and/or dose modification
- AEs leading to study drug discontinuation
- SAEs

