7.8. Changes from Protocol-Specified Safety Analyses

There are no deviations from the protocol-specified safety analyses.

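### SAP 7.1.5.1 drops worsening from the protocol's treatment-emergent definition and adds a discontinuation rule, yet SAP 7.8 declares no deviation

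*SAP*

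**What the plan says.** Protocol 8.6.2 gives the definition: "A treatment-emergent AE is defined as an AE that occurs or worsens in the period from the first dose of study drug", with the period running to 30 days after the last dose.

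SAP 7.1.5.1 gives a different one, with two alternatives. The first is by date: "Any AEs with an onset date on or after the study drug start date", up to 30 days after study drug is permanently stopped. The second is by outcome, whatever the onset date: "Any AEs leading to premature discontinuation of study drug". Neither refers to a change in grade. The rules for incomplete dates in SAP 7.1.5.2 also work only on onset and stop dates.

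SAP 7.8 then states: "There are no deviations from the protocol-specified safety analyses".

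Two other places bear on which events are affected. Protocol 7.2.2 says of grading: "For each episode, the highest severity grade attained should be reported". SAP 3.1.2 sets the meaning of study drug for the whole SAP: "study drug is defined as any drug in the therapy (GS-5829 or enzalutamide) unless specified otherwise".

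**The concern.** The two definitions do not select the same events, and the SAP says nothing has changed. If the SAP is programmed as written, the clinical study report will claim conformity with the protocol while using another definition.

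Safety and tolerability are a primary objective of phase 1b. SAP Section 1 records that phase 2 was never opened, so the phase 1b safety tables are a main output of the study. SAP 7.1.6.1 builds its tables of Grade 3 or higher, GS-5829-related, serious, interruption and dose-reduction events on the treatment-emergent set. An event that misses the definition misses all of them.

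The SAP gives no reason for the change. It does keep worsening for laboratory abnormalities: SAP 7.2.2.1 counts a rise of at least one grade from baseline, in line with Protocol 8.6.3. Only adverse events lost the rule, which suggests an oversight.

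**Working it through.** The plan states no figure on this point and no arithmetic applies. The check is to run each type of event through both definitions.

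**What reaches the AE form before first dose.** Protocol Section 6 and Sections 6.4.1 and 7.3.1 limit it to serious events and events related to protocol procedures. Other occurrences in screening go to medical history. Protocol 6.2.8 is broader and has any event after consent recorded. Protocol 7.1.1 makes a pre-existing event that increases in severity an adverse event in its own right.

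**How a worsened event is dated.** Protocol 7.2.2 asks for one highest grade per episode. No section says that a rise in grade opens a new record with a new onset date, and none says that it does not. The eCRF completion guidelines to which Protocol 7.3.3 and 7.3.4 refer are not among the documents.

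**Outcome by type of event** (all within the 30-day limit):

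| Event | Protocol 8.6.2 | SAP 7.1.5.1 |
|---|---|---|
| Onset on or after first dose | Counted | Counted |
| Pre-dose onset, one record, worsens on treatment, no discontinuation | Counted | **Not counted** |
| Pre-dose onset, worsens, leads to discontinuation | Counted | Counted (second alternative) |
| Pre-dose onset, does not worsen, leads to discontinuation | Not counted | **Counted** |
| Pre-dose onset, worsening entered as a new record with its own date | Counted | Counted |
| Medical-history condition that worsens after dosing, entered as an AE dated at worsening | Counted | Counted |
| Onset in the enzalutamide lead-in, worsens after GS-5829 starts | Counted | Counted, because study drug includes enzalutamide |

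The definitions part in two rows, in opposite directions. The second row is the loss. On the narrow collection rule it consists of pre-dose serious events and procedure-related events; on the wording of Protocol 6.2.8 it could include any event after consent. The fourth row is an addition that the protocol does not provide for.

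**What remains visible.** SAP 7.1.6.1 lists all adverse events with a treatment-emergent flag. It also lists all Grade 3 or higher events, all serious events and all events leading to death, none of them restricted to treatment-emergent events. An event in the second row would appear in the listing, flagged as not treatment-emergent, but in no treatment-emergent count.

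**The case against.** The strongest reply is that the loss is inferred. Protocol 7.2.2 says which grade to report; it does not define an episode or fix an onset date. Protocol 7.1.1 may point towards a new adverse event at worsening, and if sites recorded it that way, the SAP rule already captures it. Few pre-dose events reach the AE form, and several kinds of worsening are captured by other routes. This stands as to size. It does not remove the conflict between Protocol 8.6.2 and SAP 7.1.5.1, or make SAP 7.8 correct.

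A second reply concerns the remedy. If the database holds only the highest grade of each episode, a comparison of pre-dose with post-dose grade may not be programmable. An instruction to sites on recording would come too late, since SAP Section 1 says all subjects have stopped study drug and had their safety follow-up visit. Both points stand, so restoring the wording may not be enough without a check of the records.

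A reader might infer that every event present before dosing and worse afterwards would vanish from the safety report, or that the dose decisions are compromised. The documents support neither. The table above limits the loss to one type of record, and the listings still show it. Dose-limiting toxicity has its own definition and 28-day window in Protocol 3.2, is reviewed by the Safety Review Team, and is listed separately under SAP 7.1.7.1. Nothing shows that a DLT or MTD decision depends on the treatment-emergent flag.

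**Conclusion.** The point holds as a conflict between the documents with a narrow effect on the tables. SAP 7.1.5.1 omits one part of the protocol definition and adds another, and SAP 7.8 is wrong to report no deviation. That much is true even if no subject is affected.

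The effect on counts rests on an assumption: that at least one event with pre-dose onset was kept as a single record, worsened on treatment and did not lead to discontinuation. The documents neither confirm nor exclude this. The number of such events cannot be derived from them and is probably small. It is tempting to express the effect as one subject out of a cohort of three to six, but that only gives the weight of one subject and is no estimate of how many are affected. The point is minor, and worth correcting because correction is cheap.

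**What to change.** 1. Add to SAP 7.1.5.1 those adverse events with onset before the first dose of study drug that worsen in severity on or after first dose and up to 30 days after last dose.
2. Before the database is finalized, identify AE records with pre-dose onset that continue past first dose. Where the eCRF holds no pre-dose grade, query whether the event worsened.
3. Correct SAP 7.8 to declare the added discontinuation rule and any remaining difference from Protocol 8.6.2. If the SAP is already final, document the change in the clinical study report, as SAP Section 1 requires.

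The cost is a few lines of text, one data check on what should be a short list of records, and possibly a few site queries. No new data collection from subjects is needed.
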